### **Confidentiality and Ethical Issues**

All program staff, RAs, GSRs, and MSC trainers must follow confidentiality and ethical procedures throughout this program to ensure that everybody is treated with respect and dignity.

• Communication with study participants must remain confidential. To maintain confidentiality for participants, any personal information provided, such as participants' name, age, etc., will be protected by use of subject code on all data and questionnaires and stored on REDCap on the UCLA server and never anywhere else. Data including subject identifiable information will be linked to a code on RedCap for this study for access and only UCLA-approved staff, RAs, or GSRs will have access though a password-protected login.

### **Program Team**

The Graduate Student Researchers (GSRs) will help the PI ([name]) in organizing all aspects of the study. These individuals will be current graduate students in the UCLA Jonathan and Karin Fielding School of Public Health. They will be responsible for tracking recruitment, scheduling research assistants, and ensuring that the site is well-stocked with necessary supplies. Weekly, the GSRs will meet with [name] to review all aspects of the study, troubleshoot any obstacles, participate in ongoing training, and create schedules for the other RAs. The RAs will be highly trained undergraduate students from the University of California, Los Angeles.

### Safety of Program Staff

While we believe that conducting this study is highly important for public health, it is critical that the research team prioritizes their own safety first. If any member of the research team feels that they are in danger (physically, emotionally, psychologically) in any way, they will be instructed to end the study activities and inform the research coordinator or the PI as soon as it is safe to do so. This is particularly important during COVID-19 and ongoing viral outbreaks. Exposures will be promptly reported to the PI and any applicable UCLA protocols will be strictly followed.

### **Subsection 2.2 - Phase II Scope of Work & Participant Flow Diagram**

#### 1. General Recruitment

- a. We will recruit ~8 cohorts of 24-26 WEH from Prototypes, a HealthRIGHT 360 RDTS. The RDTS staff will assist the PI and GSRs in providing a minimum of two informational meetings (advertised through flyers and verbally by staff) for interested women where they will be informed about the opportunity.
- b. [name], GSRs, or RAs will administer an eligibility screener to participants using an iPad and will collect the data using REDCap.
  - i. Key inclusion criteria are subthreshold or threshold PTSD as measured by the PCL-5 PTSD screener and no cognitive impairment as measured by the Short-Blessed Test.
- c. All participants who complete the screener will receive \$5.
  - i. Note: those who complete the screener must complete the consent to screen, but are not assigned a participant ID at this time as they have not completed the Informed Consent. As such, it is imperative that accurate information be obtained with respect to the individual's name as that will be used to link it to their subsequent data. This will be stored on REDCap on the UCLA secured server and never anywhere else.
- d. Eligible WEH who wish to participate will be invited back within the next week for enrollment and baseline assessments. The research team will review the informed consent with the potential participant and provide a copy for them to take for review. Potential participants will be given 24 hours to review the document before enrolling in the study and completing baseline measures; participants are free to waive this waiting period at their own discretion.

### 2. Group Assignment and Intervention Procedure

a. Cohorts of participants will be randomized to an adapted MSC course or TAU prior to enrollment of the first participant. Consistent with the cluster design, randomization will occur at the level of the cohort rather than the participant. This design was chosen to avoid contamination within the cohorts, since participants

reside at the same RDTS. There will be eight cohorts in total, each with two intervention groups of 12-14 WEH. Each cohort will receive the same intervention (e.g., in Cohort 1 there will be two groups of MSC, in Cohort 2 there will be two groups of TAU). See **Table 2** below:

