### **Subsection 1A.4 Phase II Timeline**

Table 3. Study Timeline												
Year 1												
Month	1	2	3	4	5	6	7	8	9	10	11	12
Stud	y st	art up	Phase 1	: CAE	3 & FC	GS		Phase	II: Col	nort 1	Coho	rt 2
Year 2												
Month	1	2	3	4	5	6	7	8	9	10	11	12
		Cohor	t 3		Cohor	t 4		Coho	t 5		Coho	ıt 6
Year 3												
3.5 4	_											10
Month	1	2	3	4	5	6	7	8	9	10	11	12
Month	1	2 Cohor		•	5 Cohor		7	_	-	10 Dissemi		12

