**Table 2: Group Assignment Flowchart** 

	Intervention	
	MSC	TAU
Cohort 1	Group 1 (12-14 WEH) Group 2 (12-14 WEH)	
Cohort 2		Group 3 (12-14 WEH) Group 4 (12-14 WEH)
Cohort 3	Group 5 (12-14 WEH) Group 6 (12-14 WEH)	
Cohort 4		Group 7 Group 8
Cohort 5	Group 9 Group 10	
Cohort 6		Group 11 Group 12
Cohort 7	Group 13 Group 14	
Cohort 8		Group 15 Group 16

- b. Informed Consent: Interested and eligible women will complete informed consent at a private location at the RDTS with the PI, a GSR, or a RA. Only the PI and GSR can sign the informed consent so undergraduate RAs may answer questions about the informed consent but final signatures must be obtained from the PI or GSR.
- c. Baseline questionnaire administered:
  - i. After informed consent, participants will complete an assisted psychosocial interview to measure primary outcomes (PTSD and substance use), secondary outcomes (anxiety, depression, hopelessness, ), mediators (emotion-regulation, self-compassion, moral injury, trauma-related guilt, trauma-related shame, craving, mindfulness), and covariates (e.g., negative life

events).

- ii. GSRs and RAs will verbally read questions with response options provided both verbally and on a response card and record responses on iPads using REDCap, accessed through a password. Data will be immediately transferred to UCLA's secure server.
- iii. Women will receive \$15 for completing the baseline assessment.
- d. Locator Guide: This is a critical part of maintaining contact with our participants. However, they may not be inclined to provide all the information on the first or second meeting. NOTE TO RESEARCH ASSISTANTS: PLEASE TAKE THE PICTURE AT THE TIME OF (IMMEDIATELY AFTER) ADMINISTERING INFORMED CONSENT. Note that the picture (like any measure) is optional and participants can refuse the picture and still participate in the study.

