### **Subsection 2.4 - Phase II Recruitment & Screening**

Women will be recruited from Prototypes, a HealthRIGHT 360 RDTS. The RDTS staff will assist the PI and GSR in providing approximately two informational meetings (advertised through UCLA IRB-approved flyers and verbally by staff) for interested women where they will be informed about the opportunity. Recruitment flyers will also be posted around the RDTS. GSRs and RAs will help recruit women and conduct the initial screening in a private room or in an area onsite where the interview can not be overheard by others after completing the Consent to Screen Script. Progress will be monitored closely by [name] the Lab Management team.

There will be eight cohorts in total, each with two intervention groups of 12-14 WEH (see Table 2). Each cohort will receive the same intervention (e.g., in Cohort 1 there will be two groups of MSC, in Cohort 2 there will be two groups of TAU). The cohorts will be divided into two smaller groups of 12-14 WEH (24-26 per cohort) rather than one large group of 24-26 WEH. Recruitment and the intervention for each cohort will take approximately 6-8 weeks to complete.

[name] and/or lead GSR(s) will explain the study during an initial meeting with potential participants and answer any questions. Then women will be screened for eligibility. Prior to obtaining any data, the women will provide a "consent to screen". This is because we need to obtain data from the women to determine if they are eligible, but they are not officially enrolled as human subjects. By providing their "consent to screen", we are obtaining verbal consent/permission to ask them questions. Their data will not be used by the research team if they are not eligible.

A member of the research team will read the consent to screen script exactly as written on REDCap. Potential participants are free to stop at any time – remind them that all procedures are completely voluntary. [name] and/or someone from the Lab Management team (e.g., GSR) will always be onsite to help answer questions.

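### Arms are set before each cohort enrols, and no visible step withholds a cohort's arm from recruiters, interviewers or women until its baseline is complete

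*Combined protocol and SAP*

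**What the plan says.** Subsections 2.1 and 2.2 place allocation ahead of recruitment: "Cohorts of participants will be randomized to an adapted MSC course or TAU prior to enrollment of the first participant". Allocation is by whole cohort; the text gives as an example that "in Cohort 1 there will be two groups of MSC, in Cohort 2 there will be two groups of TAU". Table 2, titled "Group Assignment Flowchart", then lists cohorts 1, 3, 5 and 7 under MSC and cohorts 2, 4, 6 and 8 under TAU.

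The same roles appear at each step before treatment:
- Recruitment and screening (Subsection 2.4): "GSRs and RAs will help recruit women and conduct the initial screening in a private room".
- Consent (Subsection 2.2, item b): the principal investigator, a graduate researcher or a research assistant conducts it. On signatures: "Only the PI and GSR can sign the informed consent so undergraduate RAs may answer questions about the informed consent".
- Baseline (Subsection 2.2, item c): "GSRs and RAs will verbally read questions with response options provided both verbally and on a response card".

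The document speaks directly to field staff. Just below Table 2 it says "NOTE TO RESEARCH ASSISTANTS: PLEASE TAKE THE PICTURE AT THE TIME OF" consent.

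The trial is described as open-label. The visible text gives no method for generating the cohort order, no holder of it and no time at which an arm is released.

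**The concern.** When clusters are allocated first and individuals are recruited afterwards, randomization alone does not protect recruitment. Anyone who knows a cohort's arm knows it for every woman approached in that cohort. Two routes to bias are then open.

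The first is who joins. Eligible women are invited back within a week of screening, so they can decline after the arm is fixed. Staff who know the arm may also, without intending to, encourage some women more than others. The prompting allowed on the screener's index event is a minor part of this route and bears on eligibility only.

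The second is the baseline score. The PCL-5 is read aloud by staff and answered in their presence. Section 3 derives the 5-point and 10-point reductions and the group-by-time contrast from that score, so an error at baseline that depends on arm enters the PTSD result directly.

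Section 3 answers imbalance with propensity scores or multilevel models for covariates that differ at baseline. That deals with measured differences. It does not reach unmeasured selection, and it takes the recorded baseline score as correct.

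**Working it through.** The plan states no figure on this point, so there is none to reproduce. The check has three parts.

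**1. Order of events.** The sequence is allocation, information meetings and screening, up to a week's wait, consent, then baseline. The phrase about the first participant may mean first in the trial or first in the cohort. Under either meaning, allocation precedes every consent and baseline in that cohort. The sections on recruitment, screening, consent and pre-intervention assessment (2.2, 2.4, 2.7) contain no withholding step. Part of Subsection 1A.2, the text just before Subsection 1A.4 and the consent pages were not available to check.

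**2. How predictable the arms are.** If Table 2 is the operative order, 8 of 8 arms are known in advance. Otherwise, suppose staff know only past arms and guess the more likely next arm. Pure chance gives 4 of 8. Full enumeration of 4:4 orders gives:

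| Scheme | Orders | Strictly alternating | Expected correct guesses of 8 |
|---|---|---|---|
| Unrestricted 4:4 | C(8,4) = 70 | 2/70 = 2.9% | 373/70 = 5.33 |
| Two blocks of four | 6 × 6 = 36 | 2/36 = 5.6% | 17/3 = 5.67 |
| Four random pairs | 2^4 = 16 | 2/16 = 12.5% | 6.0 |

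Alternation is therefore uncommon under these schemes but possible under all of them.

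**3. Sensitivity illustration; every input is assumed.** Let the reduction in PCL-5 be normal with mean m and SD s, with no true effect. Let baseline alone be recorded d points higher in one arm. The response rate at cut c in that arm then changes by

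P(N(m+d, s) ≥ c) − P(N(m, s) ≥ c).

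The cuts c = 5 and c = 10 come from Section 3. The assumed values are m = 0, 5, 10; s = 10, 12, 15; d = 1, 2, 3.

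- c = 5: from 2.5 points (m = 10, s = 15, d = 1) to 11.8 points (m = 5, s = 10, d = 3; 50.0% becomes 61.8%).
- c = 10: from 2.2 points (m = 0, s = 15, d = 1) to 11.8 points (m = 10, s = 10, d = 3).
- Continuous change from baseline: the between-arm contrast moves by d itself, 1 to 3 points.

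A lower recorded baseline would move the results the other way.

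**The case against.** **The trial is open-label.** This is true of delivery, but it does not require the arm to be known before baseline. The stated reason for allocating by cohort is contamination among women who live together, and later release leaves that protection intact.

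**Table 2 may be only a schematic.** This stands as a possibility. The sentence introducing it gives the cohorts as an example, and Subsection 2.2 elsewhere says approximately eight cohorts. A reader might infer from the alternation that cohorts are not randomized at all. The documents do not support that: they say cohorts will be randomized, and a random order can alternate. If the table is a schematic, the missing release rule remains.

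**Field staff may not use this document.** It calls itself a study protocol, and Subsection 2.14 mentions separate training materials and a teachers' manual. That research assistants read this text is an inference from the notes addressed to them. It is likely but not stated.

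**Safeguards exist.** A scripted consent to screen, response cards, and matched visits and payment in the TAU arm reduce the risk. None of them hides the arm.

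**No harm is shown.** Correct. A reader might infer that women are told their arm before baseline, or that a bias of 2 to 12 points is expected. No text says the first, and the second is an illustration whose inputs have no source in the documents.

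**Women may hear of earlier arms anyway.** This is limited. "Table 3. Study Timeline" shows four cohorts in Year 2, about one every three months, against stays of about three months.

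**Conclusion.** The point holds as a gap in procedure. Followed as written, the plan sets the arm first, gives recruitment, consent handling and the baseline interview to overlapping roles, and does not visibly withhold the arm from them or from the women. This leaves both recruitment and the baseline PCL-5 open to knowledge of the arm, which the planned adjustment cannot fully correct.

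The size and direction of any resulting bias are unknown. The point does not establish that allocation is non-random, that the order has been disclosed, or that bias has occurred. Confidence is medium, because an absence is being asserted with some text unavailable and because the status of Table 2 is not stated. It is an inexpensive improvement that should be made.

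**What to change.** **Change to make**
- State that a cohort's arm is released to recruiters, interviewers and women only after the last baseline interview in that cohort, covering both of its groups.
- Have the order held by someone who does not screen, take consent or interview.
- Remove the arms from Table 2, or label it illustrative.
- Use the same arm-neutral flyer, information meeting and consent materials for every cohort.
- Report numbers screened, eligible, refusing and enrolled by cohort.

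**Only if Table 2 is the operative order, or field staff already know the order:** generate a new concealed random order for the cohorts not yet recruited, keeping 4:4 overall. The form of restriction is the statistician's choice. The gain shrinks as cohorts run: after two, four or six alternating cohorts, 20, 6 or 2 unrestricted 4:4 completions remain.

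**Cost**
- Sample size and outcomes are unchanged.
- The list holder must be outside the principal investigator, graduate researcher and research assistant roles, since all of these screen or handle consent. A suitable role may already exist in text that was not available.
- MSC trainers must be booked provisionally.
- The documents do not say whether a cohort's two groups start together. If they would not, the first must wait for the second's baselines. That delay must be checked against the stay of about three months and the available slack.
- The slack itself is unclear. Subsection 2.4 allows 6 to 8 weeks for recruitment plus a 6-week course, leaving 0 to 2 weeks. The Subsection 1A.4 timeline implies 52/4 = 13 weeks per cohort in Year 2, leaving 13 − 6 = 7.

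Some guessing from past arms will remain, as will open-label self-report after baseline.

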**Table 2: Group Assignment Flowchart** 

	Intervention	
	MSC	TAU
Cohort 1	Group 1 (12-14 WEH) Group 2 (12-14 WEH)	
Cohort 2		Group 3 (12-14 WEH) Group 4 (12-14 WEH)
Cohort 3	Group 5 (12-14 WEH) Group 6 (12-14 WEH)	
Cohort 4		Group 7 Group 8
Cohort 5	Group 9 Group 10	
Cohort 6		Group 11 Group 12
Cohort 7	Group 13 Group 14	
Cohort 8		Group 15 Group 16

- b. Informed Consent: Interested and eligible women will complete informed consent at a private location at the RDTS with the PI, a GSR, or a RA. Only the PI and GSR can sign the informed consent so undergraduate RAs may answer questions about the informed consent but final signatures must be obtained from the PI or GSR.
- c. Baseline questionnaire administered:
  - i. After informed consent, participants will complete an assisted psychosocial interview to measure primary outcomes (PTSD and substance use), secondary outcomes (anxiety, depression, hopelessness, ), mediators (emotion-regulation, self-compassion, moral injury, trauma-related guilt, trauma-related shame, craving, mindfulness), and covariates (e.g., negative life

events).

- ii. GSRs and RAs will verbally read questions with response options provided both verbally and on a response card and record responses on iPads using REDCap, accessed through a password. Data will be immediately transferred to UCLA's secure server.
- iii. Women will receive \$15 for completing the baseline assessment.
- d. Locator Guide: This is a critical part of maintaining contact with our participants. However, they may not be inclined to provide all the information on the first or second meeting. NOTE TO RESEARCH ASSISTANTS: PLEASE TAKE THE PICTURE AT THE TIME OF (IMMEDIATELY AFTER) ADMINISTERING INFORMED CONSENT. Note that the picture (like any measure) is optional and participants can refuse the picture and still participate in the study.
  - i. The Locator Guide is stored on REDCap and updated at each contact with participant, beginning with enrollment and baseline. Participants provide their name, date of birth, email, phone number, and social media accounts. We also maintain information on the residence of the participant after they are discharged from treatment: participants nearly all transfer to a sober living home near the Prototypes facility after discharge. In our experience, most participants have a phone and can be reached on their phone or via social media if their phone is disconnected after discharge. On occasion, after discharge, participants live with a friend or family member, but in our prior experience working with this population, this is relatively uncommon.
    - 1. Participants will provide name, email(s), phone number(s), and social media account(s) for their close friends and relatives. We will prompt the participant for each potential friend or relative, starting with parents (mom, dad, stepmother, stepfather), aunts and uncles, adult children, partners (husband, wife, father of children, etc.), friends, cousins, and other. We update this at each intervention session, as participants will often disclose more information to us over time as they build trust with our team. In our experience, our participants tend to keep in touch with at least one friend or family member, even if they return to using substances and become unhoused after discharge.
    - 2. During follow-ups, GSRs will be responsible for contacting participants to schedule their follow-up appointments. We first try to contact the participant several times via phone, email, and social media accounts. If we are unable to reach the participant, we use the Locator Guide and begin to contact their friends and family members. We take detailed notes in the Locator Guide on REDCap, including dates of contact, who we talked to, and what information we obtained. If we can not reach a participant, we continue to re-contact the participant and their family until we reach the individual or unless the participant, friend, or family member requests us not to contact them again.
      - a. Another strategy we use is to track unreachable participants is to ask other participants in the program if they have spoken to the unreachable participant. Frequently, someone else in the

study will have updated contact information, know where the individual is residing, or is able to pass along our contact information so the unreachable participant can reach out to us.

#### e. Intervention

i. Participants will participate in a seven session (six sessions + retreat) adapted MSC short course administered over a 6-week timeframe or TAU. WEH will be compensated \$10 per session.

### f. Post-Intervention Follow-up

- i. Following the MSC or TAU sessions, participants will complete the psychosocial metrics that were assessed at baseline again and be compensated \$20. Psychosocial assessments for women who leave the RDTS will be administered at a location convenient for the participant (e.g., sober living home) or by Zoom.
- ii. Women in the MSC group will also be invited to participate in-depth interviews (approximately 20 minutes in length) to share their experiences with the intervention and be compensated \$10 for the interview.

### g. 4-Month Follow-Up

i. Four months after baseline (approximately 2 months after post-assessment), primary and secondary outcomes will be re-assessed, in addition to key covariates and recent negative life events. Participants will be contacted using the Locator Guide and compensated \$30. These sessions will occur in person (at a private location convenient for the participant) or over Zoom as requested by participant.

#### 3. Phase II Reimbursement

- a. Women will receive \$5 for the eligibility screener; \$15 for completing baseline measures; \$10 per session in the intervention; \$20 for the post-intervention follow-up and \$10 if they complete an additional interview; and \$30 for the 4-month follow-up.
  - i. Women are paid in cash or a Visa gift card and must sign on the iPad (via REDCap) that they have received the payment. If a virtual follow-up, the individual who provides compensation will sign. This must also be initiated, signed, and dated by the RA or GSR in charge of payment.

Subsection 2.3 - Phase II Recruitment & Treatment Overview

Table 3. O	Table 3. Overview of Phase II Assessments							
Intervention	Recruitment	Eligibility Screen	Baseline	Weekly	Post- Intervention Follow-up	4-Month Follow-up		

MSC	Info meetings with PI at RDTS	PTSD SBT a	Psychosocial questionnaires b,c,d Demographics Locator Guide e	Home practice adherence Accept & feasibility activities f	Psychosocial questionnaires b,c,d ~20-minute interview	Psychosocial questionnaire s b,c,d
TAU	Info meetings with PI at RDTS	PTSD SBT a	Psychosocial questionnaires b,c,d Demographics Locator Guide e	Short psych surveys g	Psycho-social questionnaires b,c,d	Psycho-social questionnaire s b,c,d

aPTSD, SBT=Short Blessed Test (cognitive impairment screen; >9=likely cognitive impairment); bPrimary (PTSD, substance use) & Secondary (anxiety, depression, hopelessness, loneliness) Outcomes, cMediators: emotion-regulation, self-compassion, moral injury, trauma-related guilt, trauma-related shame, craving, mindfulness; dCovariates: negative life events; cLocator Guide will be updated regularly; fUsed to provide detailed feedback on acceptability & feasibility of MSC intervention; gSurveys on attitudes, personality, other non-clinical factors. MSC=Mindful Self Compassion; TAU=Treatment as Usual

